Grade 4 Sight-threatening consequences; urgent intervention indicated; blindness (20/200 or worse).	
 Consult ophthalmologist immediately. Exclude ME and RVO. Continue follow up examination(s) (by retinal specialist if available) for ME and RVO. 	Permanently discontinue ponatinib.

ME = macular edema; RVO = retinal vein occlusion; RH = retinal haemorrhage. SAE = serious adverse event
 * If visual changes are clearly unrelated to study treatment (e.g., allergic conjunctivitis), monitor closely but ophthalmic examination is not required.
 * If ocular toxicities do not resolve within 14 days, permanently discontinue ponatinib.

Dose modification for neuropathy

CTCAE Grade	Action and Dose Modification
Grade 1 or transient Grade 2	No intervention
Grade 2 lasting \geq 7 days	
Hold ponatinib Resume at 45 mg after recovery to \leq grade 1
 
Recurrence at 45 mg: Hold ponatinib Resume at 30 mg after recovery to \leq grade 1
 
Recurrence at 30 mg: Hold ponatinib Resume at 15 mg after recovery to \leq grade 1
 
Recurrence at 15 mg: Discontinue ponatinib

Grade 3 or 4	
Hold ponatinib Resume at 30 mg after recovery to \leq grade 1
 
Recurrence at 30 mg: Hold ponatinib Resume at 15 mg after recovery to \leq grade 1
 
Recurrence at 15 mg: Discontinue ponatinib

Dose Modifications for reduced left ventricular ejection fraction (LVEF).

Severe congestive heart failure (CHF) and left ventricular (LV) dysfunction have been reported in patients taking ponatinib. Patients should be monitored carefully for signs or symptoms consistent with cardiac failure. ECHOs must be performed at regular intervals as outlined in the Study Calendar. The same procedure (either ECHO or MUGA, although ECHO is preferred) should be performed at baseline and at follow-up visit(s). Consider discontinuation of ponatinib in patients who develop serious CHF.

Symptoms	LVEF-drop (%) or CTCAE grade	Action and Dose Modification
Asymptomatic	Absolute decrease of >10% in LVEF compared to baseline and ejection fraction below the institution's LLN.	
 • Interrupt ponatinib and repeat ECHO within 4 weeks. • If the LVEF recovers within 4 weeks (defined as LVEF \geqLLN and absolute decrease \leq10% compared to baseline): 
 – Restart treatment with ponatinib at reduced dose by one dose level. – Repeat ECHO 4 and 12 weeks after re-start; continue in intervals of 12 weeks thereafter. • If LVEF does not recover within 4 weeks: 
 – Consult with cardiologist. – Permanently discontinue Ponatinib. – Repeat ECHO after 4, 8, 12 weeks or until resolution.
Symptomatic^b	
 • Grade 3: resting LVEF 39-20% or >20% absolute reduction from baseline • Grade 4: Resting LVEF \leq20%. 	
 • Permanently discontinue ponatinib. • Report as SAE. • Consult with cardiologist. • Repeat ECHO after 4, 8, and 12 weeks or until resolution.

^a Symptoms may include: dyspnea, orthopnea, and other signs and symptoms of pulmonary congestion and edema.

Treatment delays at the start of treatment that are unrelated to drug will require restaging of the patient and re-initiating treatment. If at any time during the course of the trial, treatment is delayed over 3 weeks due to events unrelated to drug, treatment will resume as normal once the patient is deemed stable to continue.

Dose Modifications for General Non-hematologic Toxicities

CTCAE Grade	Action and Dose Modification
-------------	------------------------------

Grade 1 or transient Grade 2	No intervention
Grade 2 lasting \geq 7 days with optimal care	Hold ponatinib Resume at 45 mg after recovery to \leq grade 1 Recurrence at 45 mg: Hold ponatinib Resume at 30 mg after recovery to \leq grade 1 Recurrence at 30 mg: Hold ponatinib Resume at 15 mg after recovery to \leq grade 1 Recurrence at 15 mg: Discontinue ponatinib
Grade 3 or 4	Hold ponatinib Resume at 30 mg after recovery to \leq grade 1 Recurrence at 30 mg: Hold ponatinib Resume at 15 mg after recovery to \leq grade 1 Recurrence at 15 mg: Discontinue ponatinib

Dose Modification for concurrent strong CYP3A inhibitors

The recommended dose should be reduced to 30 mg once daily when administering ponatinib with strong CYP3A inhibitors (e.g., boceprevir, clarithromycin, conivaptan, grapefruit juice, indinavir, itraconazole, ketoconazole, lopinavir/ritonavir, nefazodone, nelfinavir, posaconazole, ritonavir, saquinavir, telaprevir, telithromycin, voriconazole). Patients taking concomitant strong inhibitors may be at increased risk for adverse reactions.

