3. PATIENT SELECTION

3.1 Eligibility Criteria

- 3.1.1 Patients with histologically or cytologically confirmed diagnosis of refractory metastatic solid tumor for whom no other standard treatment options are available.
- 3.1.2 Patients must have tumor suitable for biopsy (as assessed by trained specialists in interventional radiology) and medically fit to undergo a biopsy or surgical procedure; OR archival tumor specimen of biopsied tumor; OR if patients do not have a tumor suitable for biopsy but have another tissue (preferably progressive metastatic site) available for molecular evaluation (*biopsy will be performed through OSU-13053 study or the UM Precision Cancer Study*).

3.1.3 Patients must have activating genomic alterations in *FGFR* (mutations, fusions or amplifications (> 6 copies)) or activating genomic alterations in *KIT*, *PDGFR α* , *RET*, *ABL1* and *FLT3* by any validated CLIA-certified molecular testing (FISH, PCR or sequencing data are acceptable). CLIA validated results from other institutions; diagnostic labs (e.g. foundation medicine) are acceptable.

3.1.4 Patients with solid tumors must have measurable disease (RECIST 1.1), defined as at least one lesion that can be accurately measured in at least one dimension (longest diameter to be recorded for non-nodal lesions and short axis for nodal lesions) as ≥ 20 mm with conventional techniques or as ≥ 10 mm with spiral CT scan, MRI, or calipers by clinical exam. Note: This trial is open only to patients with solid tumors.

3.1.5 Patients older than or equal to 18 years of age (The safety and efficacy of ponatinib in patients less than 18 years of age have not been tested).

3.1.6 ECOG performance status ≤ 1 (Karnofsky $\geq 80\%$, see Appendix A).

3.1.7 Life expectancy of greater than 3 months.

3.1.8 Patients with multiple malignancies remain eligible.

3.1.9 Patients with an inherited cancer syndrome or a medical history suggestive of an inherited cancer syndrome remain eligible.

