3.1.10 Patients must have controlled blood pressure with a systolic blood pressure < 140 mmHg and diastolic < 90 mmHg (for patients with an elevated initial BP reading (hypertensive range), a repeat measurement at least 2 minutes later should be performed, and the two readings should be averaged to obtain a BP reading). Any hypertensive at-home blood pressure reading will be confirmed in clinic. Patients on anti-hypertensive medications are eligible, if blood pressure is controlled. Study drug dosing will be interrupted for any reading $\geq 160/100$, as outlined in management table in Section 6 of the protocol.

3.1.11 Ponatinib can cause fetal harm when administered to a pregnant woman based on its mechanism of action and findings in animals. For this reason women of child-bearing potential and men must agree to use adequate contraception (hormonal or barrier method of birth control; abstinence) prior to study entry and through 4 months after the end of treatment. For females of childbearing potential, a negative pregnancy test must be documented prior to registration.

3.1.12 Patients must have normal organ and marrow function as defined below:

- Absolute neutrophil count $\geq 1,500/\text{mcL}$
- Platelets $\geq 75,000/\text{mcL}$
- Total bilirubin $\leq 1.5 \times$ upper limit of normal (ULN), unless due to Gilbert's syndrome (< 5 if liver involvement with primary tumor)
- Serum lipase and amylase $\leq 1.5 \times$ ULN

- AST(SGOT)/ALT(SGPT) $\leq 2.5 \times$ institutional upper limit of normal
- LVEF $\geq 50\%$ by ECHO or MUGA
- Serum creatinine ≤ 1.5 mg/dL *OR* calculated creatinine clearance (Cockcroft-Gault formula) ≥ 60 mL/min *OR* 24-hour urine creatinine clearance ≥ 60 mL/min

3.1.13 Patient has the ability to swallow oral medication and keep a pill diary

3.1.14 Ability to understand and the willingness to sign a written informed consent document.

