Recommended management: Anti-emetics.

Dose Modification for Diarrhea

Diarrhea is a common side effect of ponatinib. The use of anti-diarrheal medications is permitted. Patients who experience ≥ grade 2 diarrhea may begin loperamide (4 mg orally x 1, then 2 mg orally after each loose stool).

CTCAE Grade	Action and Dose Modification
≤ Grade 1	No change in dose
Grade 2	Occurrence at 45 mg: • Interrupt ponatinib and resume at 45 mg after recovery to ≤ Grade 1 Occurrence at 30 mg: • Interrupt ponatinib and resume at 30 mg after recovery to ≤ Grade 1 Occurrence at 15 mg: Discontinue ponatinib
Grade 3	Occurrence at 45 mg: • Interrupt ponatinib and resume at 30 mg after recovery to ≤ Grade 1 Occurrence at 30 mg: • Interrupt ponatinib and resume at 15 mg after recovery to ≤ Grade 1 Occurrence at 15 mg: Discontinue ponatinib
Grade 4	Off protocol therapy

CTCAE Grade	Action and Dose Modification
**Patients requiring > two dose reductions should go off protocol therapy.	Recommended management: Loperamide antidiarrheal therapy Dosage schedule: 4 mg at first onset, followed by 2 mg with each loose motion until diarrhea-free for 12 hours. Adjunct antidiarrheal therapy is permitted and should be recorded when used.

Dose Modifications for Hepatic Toxicity

Hepatotoxicity, most commonly manifested by reversible transaminase and alkaline phosphatase elevation and hyperbilirubinemia, has been observed in patients taking ponatinib. Monitoring of hepatic function is recommended and management of laboratory abnormalities should be managed with dose interruption and/or dose reduction according to the dose modification table.

CTCAE Grade	Action and Dose Modification
Elevation of liver transaminases > 3 x ULN* or alkaline phosphatase > 2.5 x ULN (Grade 2 or higher; or alkaline phosphatase > 4x ULN if related to metastatic disease limited to liver [e.g. cholangiocarcinoma])	
Occurrence at 45 mg:
 
 • Interrupt ponatinib and monitor hepatic function • Resume ponatinib at 30 mg after recovery to ≤ Grade 1 (< 3 × ULN) 
Occurrence at 30 mg:
 
 • Interrupt ponatinib and resume at 15 mg after recovery to ≤ Grade 1 
Occurrence at 15 mg:
 
 • Discontinue ponatinib
Elevation of AST or ALT ≥ 3 x ULN concurrent with an elevation of bilirubin > 2 x ULN and alkaline phosphatase > 2 x ULN	Discontinue ponatinib

Dose Modifications for Myelosuppression

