While myelosuppression can occur any time during treatment, its onset most commonly occurs within the first month on treatment. Ponatinib has not been studied in solid tumor patients and whether (or to what extent) myelosuppression will occur in these patients is unknown.

	Action and Dose Modification
Absolute Neutrophil Count (ANC) < 1 x 10 ⁹ /L Or Platelets < 50 x 10 ⁹ /L	
First Occurrence
 
 • Interrupt ponatinib and resume initial dose after recovery to ANC ≥ 1.5 x 10⁹/L and platelet ≥ 75 x 10⁹/L 
Second Occurrence
 
 • Interrupt ponatinib and resume at 30 mg after recovery

	Action and Dose Modification
	
to ANC $\geq 1.5 \times 10^9/L$ and platelet $\geq 75 \times 10^9/L$
 
Third Occurrence
 
 • Interrupt ponatinib and resume at 15 mg after recovery to ANC $\geq 1.5 \times 10^9/L$ and platelet $\geq 75 \times 10^9/L$

Dose Modifications for Hemorrhage

Concomitant use of ponatinib with anticoagulants should be approached with caution in patients who may be at risk of bleeding events. Serious bleeding events, including fatalities have been reported in patients treated with ponatinib. Most hemorrhagic events, but not all, occurred in patients with grade 4 thrombocytopenia. Interrupt ponatinib for serious or severe hemorrhage and evaluate.

CTCAE Grade	Action and Dose Modification
Grade 1	No intervention
Grade 2	
Occurrence at 45 mg:
 
 • Interrupt ponatinib and resume at 30 mg after recovery to \leq Grade 1 
Occurrence at 30 mg:
 
 • Interrupt ponatinib and resume at 15 mg after recovery to \leq Grade 1 
Occurrence at 15 mg:
 
 • Discontinue ponatinib
Grade 3 or 4	Permanently discontinue ponatinib

Dose Modifications for Pancreatitis / Lipase Elevations

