Pancreatitis (symptomatic abdominal pain associated with pancreatic enzyme elevation) and/or elevations in lipase and amylase are known AEs associated with ponatinib. Most cases of pancreatitis or elevated pancreatic enzymes occur within the first 2 months of treatment with ponatinib. Patients with low-grade (1 or 2) elevation in enzymes can be continued without dose reduction but should be monitored closely with serial enzyme level determinations. Patients can continue with ponatinib treatment at the same or a reduced dose once the event has improved to grade 1 or resolved. See below for dose-modification guidelines.

CTCAE Grade	Action and Dose Modification
Asymptomatic Grade 1 or 2 elevation of serum lipase	Consider interruption or dose reduction of ponatinib
Asymptomatic Grade 3 or 4 elevation of lipase ($> 2 \times$ ULN*) or asymptomatic radiologic pancreatitis (Grade 2 pancreatitis)	
Occurrence at 45 mg:
 
 Interrupt ponatinib and resume at 30 mg after recovery to \leq Grade 1 ($< 1.5 \times$ ULN) 
Occurrence at 30 mg:
 
 Interrupt ponatinib and resume at 15 mg after recovery to \leq Grade 1 
Occurrence at 15 mg:
 
 Discontinue ponatinib
Symptomatic Grade 3 pancreatitis	
Occurrence at 45 mg:
 
 Interrupt ponatinib and resume at 30 mg after complete resolution of symptoms and after recovery of lipase elevation to \leq Grade 1 
Occurrence at 30 mg:
 
 Interrupt ponatinib and resume at 15 mg after complete resolution of symptoms and after recovery of lipase elevation to \leq Grade 1 
Occurrence at 15 mg:
 
 Discontinue ponatinib
Grade 4 pancreatitis ($> 5 \times$ ULN of lipase)	Discontinue ponatinib

*ULN = Upper Limit of Normal for the lab

Dose Modifications for Skin Rash

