11.1.2 Disease Parameters

Measurable disease. Measurable lesions are defined as those that can be accurately measured in at least one dimension (longest diameter to be recorded) as ≥ 20 mm by chest x-ray or as ≥ 10 mm with CT scan, MRI, or calipers by clinical exam. All tumor measurements must be recorded in millimeters (or decimal fractions of centimeters).

Note: Tumor lesions that are situated in a previously irradiated area may be considered measurable.

Malignant lymph nodes. To be considered pathologically enlarged and measurable, a lymph node must be ≥ 15 mm in short axis when assessed by CT scan (CT scan slice thickness recommended to be no greater than 5 mm). At baseline and in follow-up, only the short axis will be measured and followed.

Non-measurable disease. All other lesions (or sites of disease), including small lesions (longest diameter <10 mm or pathological lymph nodes with ≥ 10 to <15 mm short axis), are considered non-measurable disease. Bone lesions, leptomeningeal disease, ascites, pleural/pericardial effusions, lymphangitis cutis/pulmonitis, inflammatory breast disease, and abdominal masses (not followed by CT or MRI), are considered as non-measurable.

Note: Cystic lesions that meet the criteria for radiographically defined simple cysts should not be considered as malignant lesions (neither measurable nor non-measurable) since they are, by definition, simple cysts.

‘Cystic lesions’ thought to represent cystic metastases can be considered as measurable lesions, if they meet the definition of measurability described above. However, if non-cystic lesions are present in the same patient, these are preferred for selection as target lesions.

Target lesions. All measurable lesions up to a maximum of 2 lesions per organ and 5 lesions in total, representative of all involved organs, should be identified as **target**

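### Hepatic interrupt row, Section 6.1: the one printed recovery number does not fit alkaline phosphatase (ALP), and the row has no rule for a raised, stable, tumour-related ALP at entry

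*Combined protocol and SAP*

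**What the plan says.** In Section 6.1, Dose Modifications for Hepatic Toxicity, one action cell serves two analytes. Transaminases trigger it when they exceed 3 x ULN. The ALP limb of the trigger reads: "alkaline phosphatase > 2.5 x ULN (Grade 2 or higher; or alkaline phosphatase > 4x ULN if related to metastatic disease limited to liver".

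At 45 mg the action is to interrupt, monitor, and then "Resume ponatinib at 30 mg after recovery to ≤ Grade 1 (< 3 × ULN"; no analyte is named beside the number. At 30 mg the restart condition is ≤ Grade 1 with no number. An occurrence at 15 mg means discontinuation. The text above the table says that "management of laboratory abnormalities should be managed with dose interruption and/or dose reduction according to the dose modification table". A second row stops treatment when AST or ALT is at least 3 x ULN together with bilirubin above 2 x ULN and ALP above 2 x ULN.

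On eligibility, 3.1.12 opens with "Patients must have normal organ and marrow function as defined below" and lists ANC, platelets, bilirubin, lipase and amylase, AST/ALT, LVEF and creatinine. ALP is not listed, and no exclusion criterion mentions it. Under 3.1.4 patients "must have measurable disease (RECIST 1.1), defined as at least one lesion that can be accurately measured". Section 11.1.2 classes "Bone lesions, leptomeningeal disease, ascites, pleural/pericardial effusions" as non-measurable. Bone-only disease is therefore not eligible, but bone plus a measurable site is. Section 5.2 allows bisphosphonates for bone metastases, so such patients are foreseen.

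**The concern.** There are two separate gaps in one row.

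- **Recovery number.** The printed figure equals the transaminase trigger. Applied to ALP outside liver-confined disease, it would allow restart while the ALP trigger is still met.
- **Tumour-related ALP.** The row has no rule relative to the patient's own screening value. The single allowance raises the trigger to 4 x ULN in liver-confined disease and leaves the recovery target where it was. Bone and mixed metastases have no allowance.

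At stake is dosing in individual patients. Each occurrence under this row costs a dose level (45 to 30 to 15 mg, then stop). Followed literally, a patient could lose dose, or be unable to restart, because of tumour burden and not because of the drug. In the other direction, a patient could be restarted while still above the level that called for interruption.

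**Working it through.** The plan states no figure to reproduce here. The check compares thresholds.

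**Inputs**
- Section 6.1, hepatic row: ALP trigger > 2.5 x ULN, labelled Grade 2 or higher, so ≤ Grade 1 is read as ≤ 2.5 x ULN; trigger > 4 x ULN if liver-confined; restart number < 3 x ULN at 45 mg only.
- 3.1.12: no ALP ceiling.

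**Step 1. Evaluate the row over a range of ALP values (x ULN)**

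| ALP | Trigger, not liver-confined | Trigger, liver-confined | ≤ Grade 1 | < 3 x ULN |
|---|---|---|---|---|
| 2.5 | no | no | yes | yes |
| 2.51 to 2.99 | yes | no | no | yes |
| 3.0 to 4.0 | yes | no | no | no |
| 4.1 | yes | yes | no | no |

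The grade test and the number part company only for 2.5 < ALP < 3. The band is 3 − 2.5 = 0.5 x ULN wide, and 3/2.5 = 1.20, so the number is 20% above the trigger.

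**Step 2. Compare other rows in Section 6.1 that print both values**
- "Asymptomatic Grade 3 or 4 elevation of lipase" has trigger > 2 and recovery < 1.5 x ULN: 1.5/2 = 0.75, on the safe side.
- "Interrupt ponatinib and resume initial dose after recovery to ANC" of at least 1.5, from a trigger below 1: 1.5/1 = 1.5, on the safe side of a lower limit. Platelets go from below 50 to at least 75: 75/50 = 1.5, likewise.

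In those rows recovery clears the trigger. For ALP the printed number does not.

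**Step 3. Follow two illustrative patients**
- *Bone plus measurable disease, stable ALP 2.8 x ULN since screening.* The trigger is met on Cycle 1 Day 1 (2.8 > 2.5). Recovery to ≤ Grade 1 is not reached while the value stays at 2.8. If the site used the number (2.8 < 3) and restarted at 30 mg, the trigger would be met again at once, and the 30 mg line has no number to fall back on.
- *Liver-confined disease, screening ALP 3.5 x ULN, rising to 4.1.* The trigger is met (4.1 > 4). Recovery requires ≤ 2.5, which is 3.5 − 2.5 = 1.0 x ULN below the patient's own screening value. The same holds in kind for any screening value between 2.5 and 4.

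**Step 4. How often?** The documents give no baseline ALP distribution. For context only, ALP rose in 37% of 449 leukaemia patients at any grade and in 2% at grade 3 or 4 (Section 7.2): 0.37 × 449 ≈ 166 and 0.02 × 449 ≈ 9. In the GIST study (Section 2.2.1) it rose in 10 patients, 28.6%, so n = 35. Neither source gives the share with entry values above 2.5 x ULN or with values in the 2.5 to 3 band.

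**The case against.** The strongest reply to the first gap is that ≤ Grade 1 is the operative test and the bracketed number only glosses it. The row itself calls ALP above 2.5 x ULN Grade 2 or higher, so 2.7 x ULN fails. The number matches the transaminase trigger, and the 30 mg line uses the grade alone. This largely stands. A reader might infer that the row holds two equal restart tests giving opposite decisions; the text does not support that. What remains is that the number is wrong for ALP and is not labelled as applying to transaminases.

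On the second gap, the table is headed as toxicity and its actions are keyed to an occurrence at a dose level. Section 7.1.1 treats a pre-existing condition as an adverse event when it worsens after the first dose. Section 12.1 defines toxicity as at least possibly related to treatment. The hepatotoxicity text in Section 2.2.1 asks for baseline and monthly liver tests and leaves action to clinical judgement. These lean towards not counting an unchanged value, so a reader should not conclude that the plan clearly orders such patients to be interrupted. They do not settle it, however. The lead-in sends laboratory abnormalities to the table without an attribution condition, and an exception for liver-confined disease implies that other tumour-related ALP counts.

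Divergence between sites is also limited by the two-institution design (Section 12.3) and the mandatory monthly safety call (Section 7.5.9).

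**Conclusion.** The point holds as a wording defect in one row, worth correcting but minor. The printed recovery number is unsuitable for ALP over a band of 0.5 x ULN, at the 45 mg step only. The absence of a baseline-relative rule affects eligible patients with bone plus measurable or mixed metastases and a stable ALP above 2.5 x ULN. It also affects liver-confined patients with a screening ALP between 2.5 and 4 x ULN who are interrupted above 4.

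This rests on reading the row's own Grade 2 label as the ALP boundary, and on reading the liver exception as implying that other tumour-related ALP is covered. The number of patients affected cannot be estimated from the documents. A reader might infer a loss of power or a distorted response rate. Nothing in the documents supports that: the sample size, power and decision rule in Section 12.2 do not depend on this row, and no figure is available from which to size any dose loss.

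**What to change.** Amend the interrupt row, at both the 45 mg and 30 mg steps:

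- **Recovery by analyte.** AST/ALT < 3 x ULN, as now. Keep the strict inequality, because the combined stop row starts at 3 x ULN. ALP ≤ 2.5 x ULN, or return to about the screening value if that was higher and tumour-related.
- **Occurrence.** An ALP within a small pre-stated margin of a tumour-related screening value is not an occurrence. The investigators should set the margin. Without one, ordinary assay variation (say 2.60 at screening and 2.65 on Cycle 1 Day 1) would still trigger interruption.

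Leave the transaminase trigger and the combined AST/ALT, bilirubin and ALP stop row unchanged.

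The cost is one table row in an amendment. No new test is needed: ALP is in the chemistry panel at screening and on Day 1 of each cycle (Section 10). The downside is slightly less sensitivity to an isolated drug-related ALP rise in these patients. The combined stop row does not catch such a rise by itself: with ALP above 2.5 x ULN its ALP limb (> 2 x ULN) is already met, so it turns on AST/ALT and bilirubin.

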6. DOSING DELAYS/DOSE MODIFICATIONS

6.1 Dose Modifications for Ponatinib

A maximum of two ponatinib dose level reductions are allowed. If a third dose level reduction is required, treatment will be permanently discontinued. The starting dose for ponatinib is 45 mg oral daily.

Patients who experience a vascular (arterial or venous) occlusive event should be immediately discontinued from the study and ponatinib should not be restarted. For serious reactions other than arterial or venous occlusion, do not restart until the serious event has resolved.

Dose Modifications

Dose Level	Ponatinib Dose/Schedule
0	45 mg daily
-1	30 mg daily
-2	15 mg daily

Dose Modification for Nausea

Nausea and vomiting are reported with ponatinib. The use of an antiemetic prophylactically is not recommended. However, if a patient is symptomatic, appropriate antiemetic medications may be used as clinically indicated.

CTCAE Grade	Action and Dose Modification
≤ Grade 1	No change in dose
Grade 2	Occurrence at 45 mg: 
• Interrupt ponatinib and resume at 45 mg after recovery to ≤ Grade 1 Occurrence at 30 mg: 
• Interrupt ponatinib and resume at 30 mg after recovery to ≤ Grade 1 Occurrence at 15 mg: 
• Discontinue ponatinib
Grade 3	Occurrence at 45 mg: 
• Interrupt ponatinib and resume at 30 mg after recovery to ≤ Grade 1 Occurrence at 30 mg: 
• Interrupt ponatinib and resume at 15 mg after recovery to ≤ Grade 1 Occurrence at 15 mg: 
• Discontinue ponatinib
Grade 4	Off protocol therapy

**Patients requiring > two dose reductions should go off protocol therapy.*

Recommended management: Anti-emetics.

Dose Modification for Vomiting

CTCAE Grade	Action and Dose Modification
≤ Grade 1	No change in dose
Grade 2	Occurrence at 45 mg: • Interrupt ponatinib and resume at 45 mg after recovery to ≤ Grade 1 Occurrence at 30 mg: • Interrupt ponatinib and resume at 30 mg after recovery to ≤ Grade 1 Occurrence at 15 mg: Discontinue ponatinib
Grade 3	Occurrence at 45 mg: • Interrupt ponatinib and resume at 30 mg after recovery to ≤ Grade 1 Occurrence at 30 mg: • Interrupt ponatinib and resume at 15 mg after recovery to ≤ Grade 1 Occurrence at 15 mg: Discontinue ponatinib
Grade 4	Off protocol therapy

*Patients requiring > two dose reductions should go off protocol therapy.

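### The pancreatitis/lipase text in Section 6.1 allows the same dose on restart, while the table beneath it requires a lower dose or a stop, and neither is said to govern

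*Combined protocol and SAP*

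**What the plan says.** Two rules for continuing treatment stand next to each other under the pancreatitis/lipase heading of Section 6.1.

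The text first lets low-grade (1 or 2) enzyme elevations continue without dose reduction, under close monitoring. It then says, for events in general: "Patients can continue with ponatinib treatment at the same or a reduced dose once the event has improved to grade 1 or resolved". It ends with "See below for dose-modification guidelines".

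The table has four rows:

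- Asymptomatic grade 1 or 2 lipase elevation: interruption or reduction is to be considered.
- "Asymptomatic Grade 3 or 4 elevation of lipase" (above 2 x ULN), or asymptomatic radiologic pancreatitis, labelled grade 2: interrupt, restart one level lower on recovery to grade 1 or below, and discontinue at 15 mg.
- "Symptomatic Grade 3 pancreatitis": at 45 mg, "Interrupt ponatinib and resume at 30 mg after complete resolution of symptoms and after recovery of lipase elevation to" grade 1 or below; at 30 mg, the same conditions with restart at 15 mg; at 15 mg, discontinue.
- "Grade 4 pancreatitis": discontinue.

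The opening of Section 6.1 adds a general rule: "For serious reactions other than arterial or venous occlusion, do not restart until the serious event has resolved". The background on pancreatitis in Section 2.2.1 requires full resolution of symptoms and lipase below 1.5 x ULN before any restart after pancreatitis. Neither of these gives a restart dose.

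**The concern.** The sentence and the table give different instructions for the same patient. After a grade 3 lipase elevation at 45 mg that has recovered to grade 1, the sentence permits 45 mg and the table requires 30 mg. At 15 mg, the sentence permits continuing and the table requires stopping. The sentence makes no exception for grade 4 pancreatitis, for which the table allows no restart.

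This is operative dosing text for a known toxicity: Section 2.2.1 names pancreatitis as the dose-limiting toxicity of the phase 1 study. The main stake is patient safety through re-exposure at a dose that the table rules out. A lesser stake is the tolerability summary in Section 12.4, which describes dose modifications and patients who leave treatment for adverse reactions. If sites follow different rules, the numbers of reductions and discontinuations partly reflect which rule each site used.

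**Working it through.** The plan states no figure on this point, so there is none to reproduce. The check has two parts.

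**1. Text against table**

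| Event | Text | Table | Compatible? |
|---|---|---|---|
| Asymptomatic grade 1-2 lipase | Continue without reduction | Reduction or interruption optional | Yes |
| Asymptomatic grade 3-4 lipase, or radiologic (grade 2) pancreatitis | Same or lower dose once grade 1 or resolved | 45 to 30, 30 to 15, stop at 15 mg | No |
| Symptomatic grade 3 pancreatitis | Same or lower dose once grade 1 or resolved | 45 to 30, 30 to 15, stop at 15 mg; symptoms fully resolved | No, on dose |
| Grade 4 pancreatitis | No exception stated | Discontinue | No |

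The next question is whether another provision settles the dose.

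- The pointer "See below for dose-modification guidelines" names the table but gives no order of precedence.
- The serious-reaction rule and the Section 2.2.1 restart condition govern when to restart. They do not govern the dose.
- The limit of two dose reductions in Section 6.1 acts only when a further reduction is required. Under the sentence, continuing at the same dose requires none.
- The hepatic text in the same section does tie management to its table: "management of laboratory abnormalities should be managed with dose interruption and/or dose reduction according to the dose modification table". The pancreatic text has no such clause.

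**2. How many patients the wording could reach**

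Inputs:

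- Planned patients: 30 + 15 = 45 (Section 12.3).
- GIST study (Section 2.2.1): three patients with grade 3 lipase elevation and no grade 4 events. The denominator follows from 19 patients being 54.3%: 19 / 0.543 = 35.
- Leukemia phase 2 study, grade 3 or 4 lipase elevation: 15% (laboratory table, Section 7.2) and 18% (pancreatitis text, Section 2.2.1).

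Expected number = rate x 45:

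- GIST: 3/35 = 8.6%; 0.0857 x 45 = 3.9, about 4. The exact 95% interval for 3/35 is 1.8% to 23.1%, or 0.8 to 10.4 patients.
- Leukemia: 0.15 x 45 = 6.8 and 0.18 x 45 = 8.1, about 7 to 8.

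These figures count lipase elevations. Pancreatitis is also affected, at between 0/35 (GIST) and 30/449 = 6.7% (leukemia; 0.067 x 45 = 3.0 patients). The two groups can overlap and should not be added.

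**The case against.** The best defence is that the sentence is an introduction. It is permissive, it closely follows a Section 2.2.1 sentence describing earlier patients' experience, and it leads at once into a dose-specific table. The same or a reduced dose can be read as the range across the rows, since the first row allows the same dose. It could also describe a grade 2 elevation for which treatment was interrupted. There are backstops too: Section 7.1.3 sends test results of grade 3 or higher to the principal investigator, and Section 7.5.9 requires monthly safety calls with all sites.

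Much of this stands. The table is probably meant to govern, and most sites would probably use it. But the sentence does not confine itself to low-grade events. Restart at the same dose is also normal elsewhere in Section 6.1, for example after grade 2 nausea or a first myelosuppression event, so it would not strike a site as an error. The backstops can catch a departure, but they do not say which rule is right.

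A reader might infer two stronger points, and the documents support neither.

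- *Restart before symptoms have resolved.* For pancreatitis, Section 2.2.1 and the third row of the table both require full symptom resolution, and "For serious reactions other than arterial or venous occlusion, do not restart until the serious event has resolved" covers serious events. The table also treats grade 2 pancreatitis as asymptomatic, so an event improved to grade 1 lies below that.
- *Overlapping rows at 5 x ULN.* The last row carries a lipase value in brackets, which could suggest that symptomatic grade 3 pancreatitis with very high lipase falls in two rows. The column is headed by CTCAE grade, and Section 7.3 makes CTCAE version 4.0 the grading scale, so one event cannot be both grade 3 and grade 4. Radiologic pancreatitis is labelled grade 2, and asymptomatic grade 4 lipase elevation has its own place in the second row.

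**Conclusion.** The point holds as a contradiction over restart dose and discontinuation, in a safety rule for the phase 1 dose-limiting toxicity. It covers the table's second to fourth rows. The text and the first row differ in wording on grade 1 or 2 elevations, but they do not conflict.

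The size is about 4 to 8 of 45 patients with grade 3 or 4 lipase elevation. This rests on two assumptions: that rates from the GIST and leukemia studies carry over to this population, and that a site follows the text in place of the table. The figure is therefore a ceiling on the patients whom the wording could reach and does not forecast deviations. The GIST rate comes from 35 patients and is imprecise. The exclusions for pancreatitis history, alcohol abuse, high triglycerides and raised baseline lipase or amylase (Sections 3.1.12 and 3.2.5 to 3.2.7) may lower the number further.

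The two-stage design, sample size and decision rule for Cohort A are not affected. The correction should be made because it concerns re-exposure to a drug with a known pancreatic risk and is simple to make.

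**What to change.** Make two changes to the pancreatitis/lipase text in Section 6.1:

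1. Limit the sentence on continuing at an unchanged or lower dose to asymptomatic grade 1 or 2 enzyme elevations.
2. State that for all other pancreatic events the table governs restart dose and discontinuation, in the way the hepatic text refers to its own table.

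The table itself can stay as it is. The cost is a protocol wording amendment and notice to the sites. Sample size, visits and the decision rule do not change.
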